7.8.2 Multiple Comparisons

The overall type I error rate for the study will be preserved at the two-sided 5% significance level by using a sequential (hierarchical) testing for the primary and secondary endpoints. The details will be provided in the SAP

7.8.3 Secondary Efficacy Analyses

Secondary endpoints will be analyzed based on the FAS using appropriate statistical models based on the type of endpoints.

Analyses of Secondary Endpoints

1. Monthly Migraine Responders: For each subject, a binary response variable for change from baseline in the MMDs during the last 4 weeks of the Treatment Phase relative to baseline will be set to 'YES' if a subject's % reduction is $\geq 50\%$ or 'NO' otherwise. The proportion of responders will be presented for each treatment group. The 2-sided 95% CI around the difference in proportions (SPN-538 dose minus Placebo) and the p-value from Pearson's Chi-squared Test or Fisher's Exact Test will be presented.
2. Migraine-Specific Acute Rescue Medication: The change from Prospective Baseline in the 28-day rate of migraine-specific acute rescue medication use in the last 4 weeks of the Treatment Phase will be analyzed using the same analysis method (MMRM) as for the primary efficacy endpoint. The contrast of interest will be at Month 5 for the SPN-538 group compared with placebo.
3. Total Headache Days, Duration, and Severity: The change from Prospective Baseline in the 28-day rate of total headache days, duration of headache days (migraine and non-migraine) in the last 4 weeks of the Treatment Phase will be analyzed using the same analysis method (MMRM) as for the primary efficacy endpoint. The contrast of interest will be at Month 5 for the SPN-538 group compared with placebo.

The change from Prospective Baseline in the 28-day rate for severity in the last 4 weeks of the Treatment Phase will be summarized using descriptive statistics by severity (mild, moderate, severe, very severe).

4. Onset of action: The time to first significant treatment effect in the MMDs will be based on the MMRM analysis of the primary endpoint. The first month at which a statistically significant difference in the change from baseline in 28-day MMDs is observed and maintained until the EOS between SPN-538 and placebo will be claimed as the first month for the onset of treatment effect.
5. Headache disability: The change from baseline in the Headache Disability Score as measured by PedMIDAS during the last 4 weeks of the Treatment Phase will be summarized using descriptive statistics by visit.
6. HRQoL: The change from baseline in the HRQoL as measured by the PedsQL4.0 Total Scale Score during the last 4 weeks of the Treatment Phase for the self-report and the parent-report will be summarized using descriptive statistics by visit.

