2.2 Secondary Objectives

To assess the efficacy of SPN-538 treatment on the following:

1. Responder rate with a responder defined as a subject with at least a 50% reduction in monthly migraine days (MMDs).
2. Number of days per month requiring acute rescue medication.
3. Monthly rate of total headache days (migraine and non-migraine), duration and severity.
4. Onset of action, defined as the time to first statistically significant treatment effect observed and maintained until the end of study (EOS).
5. Headache Disability Score as measured by the Pediatric Migraine Disability Assessment (PedMIDAS).
6. Health-related quality of life (HRQoL) as measured by the Pediatric Quality of Life Inventory, Version 4.0 (PedsQL 4.0), for the self-report and parent-report.

Primary Estimand

According to the International Conference on Harmonisation (ICH) E9 Addendum, the attributes of the primary estimand (target of estimation) are provided below.

1. Treatment: To compare the treatment effect of SPN-538 vs placebo.
2. Population: The population targeted for the scientific question is defined via the inclusion and exclusion criteria in children 6 to 11 years old (inclusive) with a history of migraine.
3. Variable: The primary efficacy endpoint is the change from baseline in the monthly (28-day) rate of migraine days during the last 4 weeks of the 20-week double-blind Treatment Phase relative to the Prospective Baseline Period based on the Full Analysis Set (FAS) as defined in [Section 7.3](#).
4. Intercurrent event (ICE): For subjects discontinued due to AE or lack of efficacy, missing data will be imputed using MI under the MNAR assumption. For all other missing data due to ICE, missing data will not be imputed following the treatment

[figure not shown]
policy strategy, which assumes that ICE did not occur. Methods of handling missing data are described in [Section 7.2](#).

5. Population level summary: The difference in the mean change from baseline in the monthly (28-day) rate of migraine days during the last 4 weeks of the Treatment Phase between the SPN-538 and placebo groups will be analyzed using a MMRM as discussed in [Section 7.8.1](#).

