4.4 Method of Assigning Subjects to Treatment Group

Eligible subjects will be randomized in a 1:1 ratio at Randomization Visit (Visit 3) to receive either SPN-538 or placebo. Randomization will be stratified by number of migraine days (high vs. low) at baseline to ensure treatment balance in each stratum. High monthly migraine stratum will be defined as 6 to 14 migraine days observed during the 28-day Prospective Baseline Period; and low monthly migraine stratum will be defined as 3 to < 6 migraine days during the 28-day Prospective Baseline Period.

Treatment A: Placebo

Treatment B: SPN-538

Allocation of study treatment will occur centrally via an IWRS using a randomization schedule to determine the SM assignment for each subject being randomized.

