## 6. Statistical Methods

### 6.1. General Principles

All statistical analysis, data processing, tabulation of descriptive statistics, calculation of inferential statistics, and graphical representations will be performed using SAS version 9.4 or higher.

All tabulations of analysis results will include summaries for the two treatments: SPN-538 and placebo.

Continuous variable summaries will include the number of subjects (n) with non-missing values, mean, standard deviation (SD), median, interquartile range (Q1 and Q3), minimum, and maximum.

Categorical variable summaries will include the frequency and percentage of subjects who are in the particular category or each possible value. In general, the denominator for the percentage calculation will be based upon the total number of subjects in the study population for the treatment groups, unless otherwise specified. The denominator for by-visit displays will be the number of subjects in the relevant study population with non-missing data at each study visit.

The minimum and maximum will be reported with the same degree of precision (i.e., the same number of decimal places) as the observed data. Measures of location (mean, Q1, Q3, and median) will be reported to 1 degree of precision more than the observed data and measures of spread (SD) will be reported to 2 degrees of precision more than the observed data.

Percentages will be presented to 1 decimal place, unless otherwise specified and with the following exceptions: a percentage of 0% will not be displayed (i.e., only the count of 0 will be displayed), and a percentage of 100% will be displayed with 0 decimal places.

Data collected at unscheduled time points will not be summarized but will be presented in subject listings.

Categorical variables will be analyzed using Pearson's chi-squared test or Fisher's exact test if 50% the expected cell counts <5.

Treatment comparison for all efficacy variables will be evaluated based on a two-sided significance level of 0.05.

All *P* values will be displayed in four decimals and rounded using standard scientific notation (e.g., 0.XXXX). If a *P* value less than 0.0001 occurs it will be shown in tables as <0.0001.

All collected data will be presented in listings.

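### The 50% responder test ignores the randomization stratum; it is valid, but mildly conservative if baseline migraine frequency predicts response

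*Protocol*

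**What the plan says.** Protocol 4.4, repeated in SAP 3.4.4, states: "Randomization will be stratified by number of migraine days (high vs. low) at baseline to ensure treatment balance in each stratum". The upper stratum is set out as "High monthly migraine stratum will be defined as 6 to 14 migraine days observed during the 28-day Prospective Baseline Period"; the lower one covers children with at least 3 but fewer than 6 such days.

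The first-listed secondary endpoint is response, a reduction of at least 50% in monthly migraine days from that same baseline. Under Protocol 7.8.3 item 1 the proportion of responders is shown by arm, with a two-sided 95% CI for the difference, and "the p-value from Pearson's Chi-squared Test or Fisher's Exact Test will be presented". No stratum or baseline term is mentioned for either the test or the interval.

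SAP 6.1 gives the general rule for categorical variables: Pearson's chi-squared test, or "Fisher's exact test if 50% the expected cell counts <5". SAP 6.4 brings baseline values into statistical models where relevant, but a two-by-two test has no place for one. SAP 10 reports no change from the protocol's planned analyses.

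By contrast, the primary MMRM (Protocol 7.8.1) includes baseline monthly migraine days as a covariate. Protocol 7.8.3 items 2 and 3 apply the same method to rescue medication, headache days and headache duration.

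**The concern.** Stratified 1:1 allocation removes between-stratum variation from the treatment comparison. An unstratified test still counts that variation as noise. If the strata respond differently, the variance it uses is too large: the p-value is on average somewhat too large, the interval somewhat too wide, and the actual type I error below 5%.

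The stratifier is the baseline from which percentage reduction is measured, so a link with response is plausible. The protocol also treats a reduction of at least 50% as the clinical mark of successful prevention (Protocol 3.2). It states no power for this endpoint, so there is no known margin from which to absorb a loss. At stake is a modest amount of efficiency on a clinically important secondary endpoint.

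**Working it through.** **The plan's own figure.** The sample size is for the primary endpoint: difference 1.1, SD 3, two-sided alpha 0.05, power 80%. n per arm = 2 × (1.96 + 0.842)² × 3² / 1.1² ≈ 117, and 234 / 0.85 = 275.3, so 276 randomized. Both figures reproduce. Neither concerns responders.

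**Inputs for the responder test.** From the documents: two strata, 1:1 allocation, two-sided 0.05, 117 per arm (the completer target). Assumed, because the documents give none of them: 45% versus 30% responders, strata of equal size, and a stratum gap d in responder rate that is the same in both arms.

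**Which test applies.** The pooled rate is 37.5%, so the smallest expected cell is 117 × 0.375 = 43.9. The SAP 6.1 condition for Fisher's test is not met and Pearson's test would be used.

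**Variance.** With equal strata, the within-stratum variance in each arm is p(1−p) − d²/4. Ignoring strata, the sum over arms is 0.45 × 0.55 + 0.30 × 0.70 = 0.4575.
- d = 20 points: 0.4575 − 2 × 0.01 = 0.4375. The ratio is 0.956, so variance is overstated by 1/0.956 − 1 = 4.6% and CI width by about 2.3%.
- d = 30 points: 0.4575 − 2 × 0.0225 = 0.4125. The ratio is 0.902, so variance is overstated by 10.9% and CI width by about 5.3%.

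**True size of the unstratified test.** Size = 2[1 − Φ(1.96/√(1−φ²))], where φ² = (d²/4) / (0.375 × 0.625).
- d = 20: φ² = 0.01/0.2344 = 0.043, size about 4.5%.
- d = 30: φ² = 0.0225/0.2344 = 0.096, size about 3.9% (4.0% in simulation).

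**Power at 117 per arm.** Power = Φ[(0.15 − 1.96 × SE₀)/SE₁], where SE₁ is the true standard error and SE₀ the null standard error that each test uses.
- d = 20: SE₁ = √(0.4375/117) = 0.0612. Unstratified SE₀ = √(2 × 0.2344/117) = 0.0633, power 66.4%. Stratified SE₀ = √(2 × 0.2244/117) = 0.0619, power 68.0%.
- d = 30: SE₁ = √(0.4125/117) = 0.0594. Unstratified SE₀ is again 0.0633, power 66.9%. Stratified SE₀ = √(2 × 0.2119/117) = 0.0602, power 70.5%.

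Simulation under stratified 1:1 allocation gives:

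| Stratum gap | Chi-square power | CMH power | Loss |
|---|---|---|---|
| 5 points | 66.3% | 66.4% | 0.1 |
| 10 points | 66.0% | 66.5% | 0.5 |
| 20 points | 66.8% | 67.9% | 1.1 |
| 30 points | 67.3% | 70.9% | 3.6 |

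At 138 per arm the same assumptions give 74.5% versus 75.2% at 20 points and 75.1% versus 77.7% at 30.

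**How large might the gap be?** As an illustration, take the protocol's SD of 3 for change and assume mean baselines of 4 and 8 days, so that response needs reductions of 2 and 4 days.
- Mean reduction proportional at 40% (1.6 and 3.2 days): Φ(−0.4/3) = 44.7% and Φ(−0.8/3) = 39.5%, a gap of about 5 points.
- Constant mean reduction of 2 days: 50% and Φ(−2/3) = 25.2%, a gap of about 25 points.

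So gaps from negligible to material are all compatible with what the documents state.

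**The case against.** The best defence is that a plain chi-square test is a simple, pre-specified and valid test of a marginal difference in proportions. Under balanced 1:1 allocation within strata the risk difference is unbiased, and type I error stays at or below nominal apart from discreteness. The endpoint is already scaled to each child's own baseline, which may weaken the link with the stratum. The protocol makes no power claim for this endpoint that could fail. All of this stands.

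It is also true that stratifying does not always gain power. In simulations with an overall control rate of 40% and an odds ratio of 2.1, at 117 per arm and with no stratum gap, discreteness put chi-square power at 82.3% against 80.3% for CMH. At 138 per arm the two were equal (85.9%). The number analysed may lie between these sizes, because the FAS requires only one valid post-randomization month.

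Three stronger readings are tempting but unsupported:
- A reader might infer that the test definitely loses power. That needs responder rates that differ by stratum, and neither document gives any.
- A reader might infer that a conservative miss here would block other endpoints. Protocol 7.8.2 plans hierarchical testing but leaves the details to the SAP, and the order is not visible in the SAP text available for this review. Being listed first does not establish a position in the hierarchy.
- A reader might infer that the SAP repeats the omission. SAP 6.1 and SAP 10 point that way, but the detailed secondary-analysis text is not visible, so a stratified analysis there can be neither confirmed nor excluded.

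What survives is the mismatch between Protocol 4.4 and 7.8.3, and the direction of its effect if the stratum is prognostic.

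**Conclusion.** The point holds as a minor efficiency and consistency matter. The design stratifies on baseline migraine days; the responder analysis, as specified in the protocol, does not use that factor. If the stratum predicts response, the test is mildly conservative and the CI slightly too wide. If it does not, apart from discreteness nothing is lost.

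Under the assumed 45% versus 30%, equal strata and 117 per arm, the cost runs from essentially nothing at gaps up to 10 points to about 3.5 power points at a gap of 30. The mismatch and the direction are certain; the size is not, because it rests on rates and stratum shares that the documents do not supply. The validity of the planned test is not in question.

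**What to change.** In Protocol 7.8.3 item 1, and in the SAP's responder analysis if its text matches, make the primary responder test a Cochran-Mantel-Haenszel test stratified by the IWRS baseline migraine-day stratum (3 to <6 versus 6 to 14). Report the Mantel-Haenszel weighted risk difference with its 95% CI, so that test and interval agree. Keep the unstratified proportions, difference and p-value as supportive.

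Specify this before unblinding, since choosing between the two tests afterwards would be data-driven. The cost is one sentence and a small programming change, with no new data.

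If the sponsor prefers to keep the plain test, a sentence acknowledging that it is deliberately unstratified, and possibly conservative, would be enough.

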7.9 Sample Size and Power Considerations

Based on data from previous studies conducted in adolescents and adults (MIGR-001, MIGR-002 and MIGR-003), a common SD of 3 is assumed for both the treatment and control groups. Assuming a treatment difference of 1.1, a sample size of 117 subjects per arm (a total of 234 subjects) will yield 80% power to detect a non-zero difference between the mean change from baseline in the MMDs between the active treatment and the placebo groups using a two-sample t-test at a 2-sided significance level of $\alpha=0.05$.

It is assumed that approximately 15% of subjects will drop-out before completing the study, hence an adjusted total sample size of 276 subjects (138 subjects per arm) will be randomized in a 1:1 ratio to obtain 234 subjects at the completion of the study.

7.11 Safety Analysis

Safety analysis as described below will be conducted using the Safety Analysis Set. All safety analyses will be performed on the Safety Analysis Set.

The incidence rate of AEs will be calculated by treatment group for each System Organ Class (SOC) and Preferred Term (PT). The severity of the AEs and the relationship to

SM will be summarized by treatment group for each SOC and PT. AEs will be summarized using discrete summaries at the subject and event level by SOC and PT, and by severity and relationship separately for each treatment group. Verbatim description and MedDRA SOCs and PTs for all AEs will be contained in the subject data listings.

All AEs occurring after randomization and throughout the study period will be recorded. For subjects who receive SM, TEAEs will be collected starting after the first dose of SM (Visit 3) to the end of the study. These AEs include those that emerge during treatment or worsen in severity during treatment. These AEs will be tabulated, listed and analyzed.

The incidence of AESIs based on AE data will be summarized for each treatment group by MedDRA SOC and PT. Supporting subject listing of AESI will be presented. For AESIs, percentages of subjects experiencing visual/ocular disturbances, oligohydrosis, hyperthermia, metabolic acidosis (serum bicarbonate), hyperammonemia, nephrolithiasis, and hepatic injury will be summarized using descriptive statistics by treatment and collection time point. Clinical laboratory values will be summarized by visit and treatment group using descriptive statistics. For quantitative laboratory parameters, both actual values and change from baseline (values collected at Screening) will be summarized.

Vital signs will be summarized by visit by treatment group using descriptive statistics. Both actual values and change from baseline will be summarized.

ECG results will be summarized by visit by treatment group using descriptive statistics (for quantitative ECG parameters) and frequency tables (for qualitative ECG parameters, including the overall ECG finding).

C-SSRS outcomes will be summarized using number and percent of subjects by categories for suicidal ideation only, suicidal behavior only and suicidality (ideation and behavior combined). The summary will be presented by treatment groups.

For physical, neurological, and eye examinations, change in status from baseline to the EOS will be summarized by body system for each treatment group.

Cognitive function will be assessed by evaluating the responses from subject responses to the cognitive questionnaire. Responses to the questions will be presented in subject listing and summarized by study visit and treatment group.

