Hematology/Chemistry/Urinalysis	X	X					X			X		X ^m	
Serum pregnancy test (FOCP only)	X												
Urine pregnancy test (FOCP only)		X	X		X		X		X	X		X	
Urine drug screen	X						X		X	X		X	

Assessments	Pre-treatment Phase		Treatment Phase								Post-treatment Phase		
	Screening ^a	Prospective Baseline	Random-ization	Titration				Maintenance			Taper (EOS) (ET)	Safety Follow up (by phone)	
Study Visit #	1	2	3	PC	4	PC	5*	PC	6,7	8	PC	9	
Day of Study Visit	-56	-28	1	14 ^b	29	43 ^b	57	71,99,127 ^b	85,113	141	148 ^b	162	169-183 ^l
Week of Study Visit	-8 to -5	-4 to -1	-		4		8		12,16	20		21-23	24 to 26
Study Visit Window	up to 4wks before V2	4wks before V3	+ 2 days		± 7 days		± 7 days		± 7 days	± 7 days		± 7 days	± 7 days
Eye Exam			X						X [V6]			X	
C-SSRS	X	X	X		X		X		X	X		X	
Concomitant medications	X ^f	X ^f	X ^f	X	X ^f	X	X ^f	X	X ^f	X ^f	X	X ^f	X ^f
Review Headache Diary		X ^g	X ^g		X ^g		X ^g		X ^g	X ^g			
PedMIDAS	X		X				X			X		X	
PedsQL 4.0			X				X			X		X	
Cognitive assessment			X				X		X	X		X	X
Dispense SM			X ^h		X		X		X	X ⁱ			
Biweekly Phone Calls				X		X		X		X	X		
AEs			X	X	X ^j	X	X ^j	X	X ^j	X ^j	X	X ^j	X ^j
SM return & adherence					X		X		X	X		X	
PK blood sampling										X ^k			
Dose reduction instruction				X		X		X			X		

AE = adverse event; C-SSRS = Columbia Suicide Severity Rating Scale; ECG = electrocardiogram; EOS = end of study; ET = early termination; FOCP = females of childbearing potential; PC = Phone Call
PedMIDAS = Pediatric Migraine Disability Assessment Questionnaire; PedsQL = Pediatric Quality of Life Inventory; PK = pharmacokinetics; SM = study medication V = Visit

* Visit 5 is end of titration and beginning of Maintenance Period of the Treatment Phase hence included within Section 5.1.5 for clarification.

- a. Subjects who had used TPM or any disallowed prophylactic migraine therapy must discontinue the treatment at least 2 weeks before the start of the Prospective Baseline Period, with an appropriate taper when applicable.
- b. Bi-weekly telephone contacts will occur between study visits, at Days 14, 43, 71, 99, 127, and 148 (± 2 days).
- c. Informed consent/assent to be obtained prior to performing any study procedures.

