5.1.1 Visit 1 – Screening (Day -56)

All reasons for screening failure will be recorded. If the subject passes screening but fails eligibility at Randomization visit (Visit 3), the reason(s) will also be recorded in the eCRF.

For subjects eligible for study participation, a Prospective Baseline Visit will be scheduled allowing for at least a 2-week/14-day washout of any disallowed migraine preventative medications the subject was receiving at Screening.

The following assessments will be conducted at this visit (screening assessments may be performed over multiple days):

- Obtain written informed consent/assent
- Obtain demographics
- Collect retrospective headache history, including non-pharmacological adjunctive treatments (last 3 months)
- Review inclusion/exclusion criteria
- Collect medical, family and psychiatric histories
- Perform physical examination (excluding genitourinary system) including height, weight and neurological examination
- Perform visual neurological exam
- Perform 12-lead ECG
- Record vital signs (pulse rate, blood pressure [BP], temperature, and respiration rate [RR])
- Collect blood samples for hematology and serum chemistry
- Collect serum sample for pregnancy testing (FOCP only)
- Collect urine sample for drug screen and urinalysis
- Administer C-SSRS
- Administer PedMIDAS scale
- Record concomitant medications

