7 STATISTICAL METHODS

7.1 General Considerations

All data will be analyzed using SAS® (SAS Institute, Inc., Version 9.3 or later).

In general, continuous variables will be summarized using standard descriptive statistics including number of subjects (n), mean (S), median, interquartile range (Q1, Q3) minimum, and maximum. Categorical variables will be summarized with frequencies and percentages.

The data summaries will be accompanied by individual subject data listings, as specified in Sections 16.2 and 16.4 of ICH Guidance E3, sorted by unique subject identifier. All data available from the electronic CRFs will be listed. Unscheduled measurements will be excluded from the descriptive statistics and statistical analysis but will be included in listings.

Categorical variables will be analyzed using categorical statistical methods such as Pearson's Chi-square test or Fisher's exact test as appropriate.

Treatment comparison for all efficacy variables will be evaluated based on a two-sided significance level of 0.05.

Unless specified otherwise, baseline is defined as the non-missing value collected most recent to and before the time of the very first dose of the SM.

Complete details of the statistical analysis will be provided in a separate SAP.

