## 4. Definitions and Derivations

- 1) Baseline: Unless specified otherwise, baseline is defined as the non-missing value collected most recent to and before the time of the very first dose of the SM.
- 2) The 28-day rate for the prospective baseline = (total number of migraine days during the last 4 weeks prior to randomization/ total number of days prior to randomization) \*28.
- 3) Headache Day is any calendar day in which the subject experiences one of the following: a qualified migraine headache, a non-migraine headache that lasts continuously for more than 30 minutes, or a headache of any duration for which acute medication was used.
- 4) Severity of Headache is rated on a scale of 0-10: 0=None, 1- 3=Mild, 4-6=Moderate, 7-9=Severe, 10=Very severe.
- 5) Migraine is defined as any headache with or without aura that meets **both A and B**

**criteria** as described below (with matched question #s in 538P401 Protocol Appendix 2 Headache Diary).

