## **9.2. Clinical Laboratory Evaluations**

Laboratory tests (chemistry, hematology, and urinalysis) will be performed at Screening, Prospective Baseline, and every visit of the Treatment Phase and Post-treatment (EOS/ET) Phase. Results will be summarized descriptively by treatment group and study visit as both observed values and change from baseline values. See Section 4 for the definition of baseline. Number and percentage of subjects with abnormal qualitative urinalysis results will be provided by treatment group and study visit.

Laboratory values for clinical chemistry and hematology will be presented by visit using descriptive statistics (n, mean, SD, median, Q1, Q3, minimum, and maximum) by treatment group for the actual and change from baseline values will be presented in Tables. If there are multiple values for a given visit, the worst value will be used for that visit.

Laboratory values for clinical chemistry and hematology will be flagged as abnormally low (L) if the value < lower limit of the normal range, normal (N) if the value is within normal range or abnormally high (H) if the value > upper limit of the normal range. In addition, shift tables for the change from baseline to all study visits and to the worst post-baseline will be presented.

Laboratory values will be displayed in the data listings and those that are outside the normal range will be flagged and presented along with corresponding normal ranges (if available). A separate listing of abnormal laboratory values will be provided. All study visits within a parameter for a subject will be presented if at least 1 study visit within that parameter has an abnormal result.

Urine pregnancy tests, urine drug screens and serum pregnancy test results will be listed separately.

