### **10. Changes from Planned Analysis**

There is no change from the planned analyses specified in the protocol.

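### Laboratory baseline is the Screening value in the protocol but the last pre-dose value in the SAP, and the SAP declares no difference

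*Protocol*

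**What the plan says.** Protocol Section 7.1 gives a default, with a proviso for exceptions: the last non-missing value before the first dose of study medication. Section 7.11 then makes an exception for quantitative laboratory parameters, to be summarised as "change from baseline (values collected at Screening".

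SAP Section 4, item 1, carries the same default: "baseline is defined as the non-missing value collected most recent to and before the time of the very first dose of the SM". It too opens with a proviso for exceptions, but the SAP makes none for laboratory data. Its laboratory section, 9.2, sends the reader back to the default: "See Section 4 for the definition of baseline".

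SAP Section 10 states: "There is no change from the planned analyses specified in the protocol". SAP Section 1 has no sentence giving either document precedence; the SAP's summary of changes records that such a sentence was deleted at FDA's request. Protocol 7.1 leaves full analysis details to the SAP but does not say that the SAP overrides the protocol.

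On washout ahead of the Prospective Baseline Period, footnote a to Protocol Table 2 reads: "Subjects who had used TPM or any disallowed prophylactic migraine therapy must discontinue the treatment at least 2 weeks before the start".

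**The concern.** The two rules pick different blood samples, and the washout lies between them. A programmer following either document would produce laboratory tables that contradict the other, and nothing in the current text settles which is right.

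The choice matters most for bicarbonate and ammonia. The protocol's Introduction names metabolic acidosis and hyperammonemia among the laboratory abnormalities attributable to topiramate, Section 6.6.9 lists both as events of special interest, and both analytes are in the panel (Protocol Table 3). A child still taking topiramate at Screening may give an on-drug value there and an off-drug value at Visit 2. SAP Section 9 plans no inferential safety tests, so the descriptive change-from-baseline and shift tables are among the main laboratory displays.

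**Working it through.** No figure in the plan needs reproducing. The check is of the text, followed by simple algebra for direction and size.

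**Which sample each rule selects**

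- Visit 1 (Screening, Day -56): Protocol 5.1.1 schedules a draw, "Collect blood samples for hematology and serum chemistry".
- Visit 2 (Prospective Baseline, Day -28): Protocol 5.1.2 schedules the same draw.
- Visit 3 (Randomization, Day 1): no hematology or chemistry in Protocol 5.1.3 or Table 2.

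| Rule | Sample | Position |
|---|---|---|
| Protocol 7.11 | Visit 1 | up to 8 weeks before Visit 3, before washout |
| SAP 9.2 with Section 4 | Visit 2 if non-missing | 4 weeks before Visit 3, after washout |

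The rules coincide only when the Visit 2 value is missing. Screening cannot be read loosely to include Visit 2, because Table 2 labels the two visits separately.

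**Timing for a child who needs washout**

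Visit 2 is at least 14 days after Screening (Protocol 5.1.1) and at most 4 weeks after it (Table 2). Visit 2 is nominally 28 days before Visit 3. The Screening sample is therefore 28 + 14 = 42 to 28 + 28 = 56 days before dosing.

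**Direction and size**

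Let f be the share taking topiramate at Screening and D the drug's effect on the analyte. Assume the full effect is present at Screening, gone by Visit 2, and present again on active study drug.

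- Visit 2 baseline: mean change is D on active and 0 on placebo.
- Screening baseline, active: D - fD = D(1 - f).
- Screening baseline, placebo: 0 - fD = -fD.
- Difference in mean change: D(1 - f) - (-fD) = D under either rule.

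The documents do not give f. With D = -1 unit (a fall, as for bicarbonate) and f assumed between 0% and 30%:

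| f (assumed) | Active | Placebo | Difference |
|---|---|---|---|
| 0% | -1.00 | 0.00 | -1.00 |
| 5% | -0.95 | +0.05 | -1.00 |
| 10% | -0.90 | +0.10 | -1.00 |
| 20% | -0.80 | +0.20 | -1.00 |
| 30% | -0.70 | +0.30 | -1.00 |

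For ammonia the signs reverse. For one affected child, the change is D - D = 0 on active and 0 - D = +1 on placebo. In a shift table, a child already low at Screening goes low-to-low on active where a Visit 2 baseline could show normal-to-low, and can go low-to-normal on placebo.

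**The case against.** A reader might infer that a Screening baseline would hide metabolic acidosis. The documents do not support that. SAP 9.1 takes AE-based events of special interest from a flag on the AE form. SAP 9.2 also gives observed values by visit, low/normal/high flags against the normal range, and a listing of abnormal values with all visits for that parameter. None of these uses baseline, so a child with low bicarbonate on study drug is still flagged.

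A reader might also extend the argument to valproic acid and every other drug that must be stopped, or put a figure in mEq/L on the bias. The documents attribute acidosis and hyperammonemia to topiramate only, and give neither the share of children on it at Screening nor the size of its effect. That share may well be small: the Introduction says topiramate is indicated for migraine only from age 12, and Exclusion 4 removes adequate-dose non-responders and children who stopped it for adverse events within 6 months.

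Randomisation follows both samples, so affected children fall in both arms and the difference in mean change is unbiased in expectation. This stands. It is a property of means: a count of normal-to-low shifts alone does not cancel in the same way, although mirror-image low-to-normal shifts would appear on placebo.

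Finally, the SAP already uses the post-washout sample, so the attenuation arises only if the protocol's rule is programmed. That is fair, but with no precedence rule and no declared change, the documents do not exclude it.

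**Conclusion.** The contradiction is in the current text of both documents, is undeclared, and holds even if no child was on topiramate at Screening. It yields two different sets of laboratory change-from-baseline and shift tables.

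Of the two rules, the protocol's is the weaker, because its sample can precede washout. The effect is limited to within-arm change and shifts in bicarbonate and ammonia among children taking topiramate at Screening: attenuation by the fraction f on active, and an apparent improvement of the same size on placebo. This assumes a full drug effect at Screening that has gone by Visit 2; a partial effect gives less. The evidence supports saying that a Screening baseline could attenuate these summaries. It does not support saying that acidosis would be missed or that the randomised comparison of mean change is biased.

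**What to change.** Preferred: in Protocol 7.11, replace the Screening parenthesis with the general rule of Protocol 7.1 and SAP Section 4 (last non-missing value before first dose, normally Visit 2), and state in SAP 9.2 that this baseline applies to laboratory change-from-baseline and shift tables.

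If the protocol is not amended: declare the difference in SAP Section 10 and state there that the last pre-dose value governs those tables.

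Either should be done before unblinding. The cost is wording only, with no added visits or samples. The first option needs an amendment or administrative change under Protocol 8.2 as well as a SAP edit; the second needs only the SAP edit. The same revision could correct SAP 9.2's statement that laboratory tests are done at every Treatment Phase visit: after randomisation, Protocol Table 2 schedules them only at Visits 5, 8 and 9.
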